We will register our trial in ClinicalTrials.gov within the timeframe specified in the NIH Policy on the Dissemination of NIH-Funded Clinical Trial Information. We will submit results of the trial to ClinicalTrials.gov no later than 1 year after participants have completed the trial, including the 6-month follow-up assessments. We will include a statement in our Consent and Assent forms regarding ClinicalTrials.gov.

MUSC's Office of Research and Integrity & Assurance Responsibilities administers ClinicalTrials.gov accounts and monitors research community activity and responsibilities within ClinicalTrials.gov. PI [name] will be responsible for creating records on ClinicalTrials.gov.

STATISTICAL DESIGN AND POWER

In the proposed study, 40 eligible participants will be initially recruited, assuming an estimated 20% dropout rate, in order to obtain data on 32 treatment completers. A moderate effect size is expected in the current study. Previous research testing visual cognitive interference tasks reported a medium effect size for models estimating craving strength ($f^2 = 0.12$; $n = 31$).⁵⁻⁶ A power analysis was conducted using G*Power 3.1 to detect a medium-sized between groups effect ($d = .50$, $\alpha = .05$) with a power of .80, a total sample of 24 is needed (i.e., 12 participants per group). However, due to this developmental nature of this study and the objectives to demonstrate preliminary efficacy, the proposed sample size is larger. The proposed study will therefore enroll 40 participants to be randomized to treatment to estimate an 80% study retention rate with a 95% confidence interval of $\pm 13\%$.

Descriptive analyses will be used to describe the sample. Clinical outcomes of interest are defined as: (1) decrease in craving measured by a single item from the Visual Analogue Scale immediately after task completion and from baseline to 2-week intervention phase (2) decrease in number of standard drinks (amount) from baseline to 2-week intervention phase and at 1-month follow-up measured by daily reports of “how many standard drinks did you consume yesterday?”. In order to establish feasibility, descriptive analyses will be used to measure the proportion of prompts participants responded to and response time to complete prompts. Intent to treat mixed-effects regression will be conducted to test differences in craving items after completing the task, nested within individuals. We will use a random effects mixed modeling approach using maximum likelihood estimation to test differences in mean craving and drinking outcomes (i.e., alcohol consumption) between baseline and post-experiment. We will also test differences in alcohol consumption between baseline and one-month follow-up. The participants will be modeled as random factors and the group allocation will be a fixed factor. We will examine the intervention between intervention and study time (baseline versus follow-up). Maximum likelihood estimation will provide unbiased estimates assuming missingness at random. [name] will be attending a summer statistical workshop in ecological momentary assessment data analysis and receive consultation from statisticians housed within the South Carolina Clinical & Translational Research Institute to support the proposed analyses in this project.

STUDY TIMELINE

| Overview of Study Timeline | | Months | | | | |
|-------------------------------------|--|--------|---|------|----|-----|
| | | 1 | 2 | 3-11 | 12 | 13+ |
| Tasks/Activities | | | | | | |
| Study Start Up | | ↔ | | | | |
| Recruitment | | | ↔ | → | | |
| Conduct Randomized Controlled Trial | | ↔ | → | | | |
| Data Cleaning/Analysis | | | ↔ | → | | |
| Dissemination | | ↔ | → | | | |

References

- ¹Substance Abuse and Mental Health Services Administration (SAMHSA). National Survey on Drug Use and Health (NSDUH). 2015 (NSDUH-2015-DS0001) Public-Use File Dataset. Available at: <https://www.datafiles.samhsa.gov/study-dataset/national-survey-drug-use-and-health-2015-nsduh-2015-ds0001-nid16894>.

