4. IMPORTANCE OF KNOWLEDGE TO BE GAINED

The potential benefits of the knowledge to be gained from the proposed study are considerable. This study proposes to test a brief visual cognitive test to reduce alcohol craving and consumption. Alcohol misuse is common and under-treatment among women. The proposed research is an essential step in informing evidence-based practices for reducing alcohol misuse among women. The plans for monitoring risk as described above warrant the conduct of this study for the knowledge that may reasonably be expected to result.

DATA AND SAFETY MONITORING (DSM)

A Data and Safety Monitoring Plan (DSMP) has been developed in accordance with the National Institutes of Health (NIH) Office of Human Research Protection (OHRP) to assure the appropriate clinical safety monitoring of study subjects participating in this study. Recruitment and safety data are monitored according to the schedule established by the monitoring board. Quality control and assurance of data entered into the database is discussed above as part of Protections Against Risk. Missing data will be considered as part of the plan for statistical analysis.

Summary of the Protocol: This application proposes to test the efficacy of a visual cognitive interference task using ecological momentary assessments to reduce alcohol craving and consumption. The primary outcomes of interest include: (1) alcohol craving, (2) alcohol consumption.

Trial Management: The study will be conducted and managed in the National Crime Victims Research and Treatment Center in the Department of Psychiatry at Medical University of South Carolina (MUSC), College of Medicine, in Charleston, SC.

Data Management and Analysis: The PI will oversee data management, quality control procedures and data analysis conducted by the PI. Data will be entered by trained research assistants directly into Redcap and exported to standard database software (SPSS; STATA). Quarterly audits of at least 10% of data entry will be completed. A detailed data analysis plan is outlined in the Statistics Analysis section of the Research Plan.

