Recruitment. In order to have 32 participants complete the proposed pilot randomized controlled trial (see power analysis) we will recruit 40 participants to accommodate for expected attrition rates of 20%. Participants will be recruited nationally from online campaigns, the community, and from primary care/Women's Health at the Medical University of South Carolina (see Letter of Support from Vice Chairman of the Department of Obstetrics and Gynecology). IRB approved research staff (e.g., [name], [name], [name]) will also meet with interested patients in a private room within Women's Health to inform them about the research study. Research staff will only meet with potential participants who indicate to someone directly involved in their clinical care (e.g., nursing staff) that they agree to talk with research staff about the study. Research staff will provide a brief overview of the study and those who are interested in learning more will be provided with a link to the online screener. Flyers will be posted throughout Women's Health to recruit potential participants. Prospective subjects will be informed of the study by someone directly involved in their clinical care via a flyer that includes research staff contact information. The candidate has used these methods successfully in the past to recruit subjects for her dissertation research in a fertility and reproductive medicine clinic. In addition, potential participants will be identified through EPIC and contacted by research staff via phone, email, and mail. IRB-approved study flyers and other approved study materials will be placed in prominent locations in MUSC and community-based clinics (e.g., Charleston Center, CDAP, Sleep and Anxiety Clinic) and central hubs (e.g. Coffee shops). All appropriate permissions will be obtained prior to displaying any recruitment materials at community-based clinics and outside of MUSC. In addition, participants from past MUSC research studies who have consented to be contacted for future research studies will be recruited via telephone screening and/or e-mails. These individuals will be referred to us via other MUSC researchers.

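### The stated sample of 24 does not follow from its inputs: a participant-level two-group comparison with d = .50, alpha .05 and power .80 needs 128, and no settings that could yield 24 are given

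*Combined protocol and SAP*

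**What the plan says.** The section Statistical Design and Power states: "A power analysis was conducted using G*Power 3.1 to detect a medium-sized between groups effect". The inputs are d = .50 and alpha .05, and the result is that "with a power of .80, a total sample of 24 is needed (i.e., 12 participants per group". Sidedness, test family, number of measurements and within-person correlation are not given.

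The section then describes the proposed sample as larger than this because the study is developmental and aims at preliminary efficacy. It sets enrolment at 40 "to estimate an 80% study retention rate with a 95% confidence interval of" plus or minus 13%. Expected dropout is 20%, which leaves 32 completers.

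The Recruitment paragraph of the Recruitment and Retention Plan refers back to the calculation: "In order to have 32 participants complete the proposed pilot randomized controlled trial (see power analysis".

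The planned analysis is a mixed model with participant as a random factor and group as a fixed factor, used "to test differences in mean craving and drinking outcomes (i.e., alcohol consumption) between baseline and post-experiment". The Summary of the Protocol, under Data and Safety Monitoring, says: "This application proposes to test the efficacy of a visual cognitive interference task". It names craving and consumption as primary outcomes. Specific Aims 1 and 2 hypothesise significantly lower values of both in the experimental group.

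**The concern.** Twelve per group is far below what a medium standardised difference between two independent groups normally requires, so the figure needed checking.

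This is the only power statement in the document. Because 24 is presented as sufficient and the actual sample as larger, the IRB, the sponsor and the DSMB are told that the trial exceeds what its efficacy tests need. If that is untrue for the comparison named, a null result could be misread as evidence against a medium effect when the trial had little chance of detecting one.

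**Working it through.** **Inputs.** From Statistical Design and Power: d = 0.50, alpha = 0.05, power = 0.80, stated total 24, expected completers 32, enrolled 40. Allocation is 1:1 (Human Subjects Involvement, Characteristics, and Design).

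**1. The comparison as described.** For two independent groups of n, power is the probability that a noncentral t with 2n − 2 degrees of freedom and noncentrality δ = d·√(n/2) exceeds the critical value.

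- Normal approximation, two-sided: n = 2(1.960 + 0.842)²/0.50² = 62.8, so 63 per group and 126 in total.
- Exact t, two-sided: 63 per group gives .795 and 64 gives .801, so **128 in total**.
- Exact t, one-sided: 50 per group gives .799 and 51 gives .806, so **102 in total**.

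Results at the plan's own sample sizes:

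| Total N | δ at d = .50 | Power, two-sided | Power, one-sided | d for 80% power, two-sided |
|---|---|---|---|---|
| 24 | 1.225 | .216 | .324 | 1.20 |
| 32 | 1.414 | .278 | .396 | 1.02 |
| 40 | 1.581 | .338 | .463 | 0.91 |

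The 95% confidence interval on a standardised difference has half-width of about t·√(2/n). That is 2.042·√(2/16) = 0.72 at 32 women and 2.024·√(2/20) = 0.64 at 40.

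**2. Attempts to reproduce 24 by other simple routes.**

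- A paired t test at 0.50 needs 34 (27 one-sided).
- Regression with one predictor and the cited f² = 0.12 needs 68.
- ANCOVA scales the 128 by 1 − r², so 24 requires r = √(1 − 24/128) = 0.90 between baseline and outcome.

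**3. Repeated-measures modules.** For two equal groups d = .50 corresponds to f = .25. In G*Power's within-between interaction, λ = f²·N·m/(1 − r), with m − 1 and (N − 2)(m − 1) degrees of freedom. With f = .25, the required N is 24 at:

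- m = 4 and r = .49 to .52 (for r = .50, λ = 0.0625·24·4/0.50 = 12.0, power .816);
- m = 3 and r = .57 to .60;
- m = 2 and r = .66 to .68.

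This f describes the group-by-time interaction, not a difference between group means. With two periods, the difference in change equals 4f, so f = .25 means 1.0 SD. A 0.5 SD difference in change is f = .125. At r = .66, .67 and .68 it needs 88, 86 and 84 women, and 24 women give power of .30 to .31.

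The between-factors module uses λ = f²·N·m/(1 + (m − 1)r). It returns 24 for f = .25 with 6 measurements and r = 0, or for f = .50 (d typed in as f) with 3 measurements and r = .50. Both give λ = 9.0 and power .818. With f = .25, m = 4 and r = .50, this module needs 82.

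**4. The planned model.** The documents give no variance components, so its power cannot be computed from them. For illustration, assume:

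- d = .50 on the single-day SD;
- complete data on 7 baseline and 14 intervention days;
- ICC of .3 to .5;
- a response to the intervention that varies between women with SD s, in single-day SD units.

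The variance of a woman's change is then (1 − ICC)(1/7 + 1/14) + s².

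| s (assumed) | Power, N = 24 | Power, N = 32 |
|---|---|---|
| 0 | .86 to .95 | .94 to .99 |
| 0.3 | .67 to .75 | .80 to .87 |
| 0.5 | .46 to .50 | .58 to .63 |

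**5. The retention statement.** For 32 of 40 the exact (Clopper-Pearson) 95% interval is 64.4% to 90.9%, with half-width (90.9 − 64.4)/2 = 13.3 points. The Wald half-width is 1.96·√(0.8·0.2/40) = 12.4 points. The stated 13% agrees with the exact interval, which is not symmetric about 80%.

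**The case against.** The strongest reply is that the plan names no t test. It plans repeated-measures mixed models on many observations per woman, so 128 is the wrong yardstick, and 24 is a legitimate output of a repeated-measures module. Part of this stands. The 128 applies only to one value per woman (or one averaged value, with d on the SD of that average). The illustration also shows that 24 could be enough for the planned contrast if response hardly varies between women. One between-factors route even corresponds to a true between-groups d of .50 on the single-occasion SD, although it needs essentially uncorrelated repeated measurements within a woman, which is implausible for craving or drinking.

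This does not rescue the sentence. Every route to 24 needs a module, a number of measurements and a correlation, and the plan gives none. The within-between routes test a different effect from the one named. Entering d as f would be an input error.

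A second reply is that this is a pilot, that the plan sets 24 aside, and that 40 rests on retention precision. That is correct, and it limits the consequence: enrolment does not depend on the figure. The wrong figure still remains as the sole power justification for the efficacy hypotheses, and the Recruitment paragraph still points to it.

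**Conclusion.** The concern holds. From the stated inputs, the total is 128 two-sided or 102 one-sided, not 24. For that comparison the expected 32 completers give about 28% two-sided power, and 80% power is reached only at d of about 1.0. These figures assume one value per woman, equal groups and a t test. The origin of 24 cannot be determined: a repeated-measures setting is possible but not stated. The power of the planned mixed model is unknown, and the ranges shown for it are assumptions. The error lies in the stated power, not in the number enrolled.

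**What to change.** Choose one of two corrections to Statistical Design and Power:

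1. Replace the sentence with correct figures, labelled as a participant-level two-group comparison: d = .50 at two-sided alpha .05 and 80% power needs 128 in total; 32 completers give about 28% power; 80% power is reached only for d of about 1.0.
2. State the G*Power module, effect size, number of measurements, correlation and sidedness actually used, and restate the result for the planned baseline-versus-intervention contrast in the units of that contrast.

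In either case, keep 40 on the retention-precision statement and say that the 13 points is the half-width of an exact, asymmetric interval. Bring the cross-reference in the Recruitment paragraph into line. Report the efficacy results as estimates with 95% confidence intervals alongside the planned tests.

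The cost is protocol wording. Sample size, enrolment and the planned analysis do not change. Option 1 states lower power than the text does now; option 2 requires recovering the original G*Power settings.

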Specific Aim 2: Evaluate the effects of a brief cognitive interference task on alcohol consumption, as measured by self-report among women who report at risk drinking. Hypothesis: Participants in the experimental group, relative to controls, will demonstrate significantly lower consumption of alcohol (fewer standard drink units) during the 2-week intervention phase and at 1-month follow-up.

Approach

Participants: Forty women who report at risk drinking will be recruited nationally from online campaigns, the community, and locally from the Women's Health Clinic at the Medical University of South Carolina (MUSC). Many women use obstetricians and gynecologists (OB/GYN) as their primary resource for behavioral health care making OB/GYN health care settings an ideal place to provide accessible interventions for AUD to women.² The inclusion criteria for alcohol consumption will be having a positive score on the AUDIT-C (i.e., a score of 3 or greater) at the time of screening. Additional inclusion criteria include: 1) female, any race or ethnicity; 2) ages 21-65; 3) able to comprehend English to provide informed consent and complete the assessments. Exclusion criteria include: 1) currently engaged in treatment for AUD; 2) current clinically significant bipolar affective disorder, schizophrenia, or psychotic disorder; 3) pregnant; 4) imminently suicidal or homicidal; 5) participants taking medications known to affect alcohol craving or consumption and 6) a score of 10 or higher on the Clinical Institute of Alcohol Withdrawal Revised (CIWA-R).²⁴

Study Procedures

Initial Screening. Potential participants will complete a brief screener over the phone or via REDCap to determine initial eligibility. The brief screener will ask yes/no and multiple choice questions focused on inclusion/exclusion criteria.

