Upon enrollment, participants will be given a full description of study procedures and asked to sign an electronic IRB-approved consent form before any additional study procedures or assessments, aside from the initial screener, are conducted. E-consent will be completed on REDCap. Participants will be sent a link to review the e-consent. Research staff will review the consent form over the phone or teleconferencing and answer any questions. Participants will be given as much time as needed to review the consent form. Participants and staff will sign the form electronically. A PDF of the completed consent form will be emailed securely to participants. Participants will complete a baseline assessment, followed by an EMA assessment period, and a post-experiment visit. To decrease risk regarding COVID-19 and increase feasibility, all study procedures will be

conducted with via telemedicine. Vidyo or doxy.me video conferencing will be used. Participants will complete study measures via a REDcap link.

Baseline Visit: The baseline visit will include interview measures that will be completed on doxy.me or vidyo, and self-report surveys completed on REDcap. Self-report measures include items from the DIAMOND¹⁸ screener, the Alcohol Use Disorder Identification Test (AUDIT),⁸ the patient health questionnaire (PHQ-9)¹⁹ and Stages of Change Readiness and Treatment Eagerness Scale (SOCRATES),⁹ Life Experiences Questionnaire²⁰, Posttraumatic Stress Disorder Checklist for DSM-5 (PCL-5)²¹, Drinking Motives Questionnaire²², the Obsessive Compulsive Drinking Scale (OCD)¹², four items assessing COVID-19 related stress, and Short UPPS-P²³. Interview measures include the Time Line Follow [name] (TLFB),⁷ substance use modules of the DIAMOND, Treatment Services Review²⁵, and for participants who screen positive for mood disorders, psychotic disorders, or suicidality will receive the corresponding modules of the DIAMOND. Eligible participants will be instructed on how to complete ecological momentary assessments (EMAs), including instructions on how to measure a standard drink and report craving. Participants will be randomized to the experimental or control condition stratified by self-report craving and depression scores. Participants assigned to the experimental condition will be instructed on how to complete the Tetris task.

[figure not shown]

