EMA Assessment Period: The current study will employ a 1-week baseline EMA period followed by a 2-week experimental EMA protocol that uses a combination of event- and signal-contingent assessments. Based on previous EMA research, participants will be instructed to initiate a morning assessment each day to assess behaviors that may not have been captured during the in-vivo assessments the previous evening (*“How many alcohol drinks did you consume yesterday?; How many alcohol drinks do you plan to consume today?”*)¹⁰. They will be provided with examples of standard drinks to help accurately assess their drinking. In addition, participants will complete the imagery subscale from the Craving Experience Questionnaire (CEQ)¹¹ to retrospectively measure their strongest episode of craving during the previous day. Participants will also be prompted once per day to complete a Cue Reactivity Ecological Momentary Assessment (CREMA). CREMA provides real-time responses to alcohol-related stimuli presented in participant’s natural environment. Participants will be randomly prompted between 2:00-9:00 PM to begin a CREMA session. Participants will have 60 minutes to respond to the prompt. Participants will complete baseline measure of craving, stress and mood, and then view a photograph of an alcoholic beverage. Each item will be presented for 30 seconds. Different photographs will be presented at each study trial. After viewing the photograph, participants will be complete post ratings of their craving, stress and mood.

Between the hours of 2:00 p.m. and 9:00 p.m., participants will receive up to three random text message prompts to complete in-vivo assessments assessing craving and mood including: “How many standard drinks have you consumed since your last assessment?; “Are you drinking alcohol right now?; “How is your mood right now?; “How stressed do you feel right now.” “How strong is your craving for alcohol right now...” An automated text message system will be used with at least 1-hour between assessments and will de-activate after an hour has expired. Participants who responded to at least 80% of the morning assessments will be invited to continue participation in the experimental portion of the study.

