During, the experimental phase, the same assessments will be administered. In addition, any occasion in which a positive response to current craving is reported, an automated prompt will be displayed to re-rate cravings four minutes later. Participants in the experimental condition will receive an automated prompted to complete the Tetris task in-between the ratings. After four minutes the application will upload a screen shot of the Tetris game into RedCAP. The Tetris task involves manipulating basic shapes to form rows that then disappear. Participants in the experimental condition will be asked to play Tetris after CREMA sessions and after any of the three random craving assessment that participants report experiencing craving. Participants in the control condition will just be asked to re-rate craving four minutes later and report what activities they completed during the three-minute break.

Post-Experiment Assessment: Participants will complete self-report questionnaires via REDCap. In addition, participants will complete the TLFB over a video call at a 1-month follow-up. Figure 1 below illustrates the study design.

Figure 1. Study design

Statistical Analyses

To establish feasibility, descriptive analyses will be used to measure the proportion of prompts participants respond to, and the response time to complete prompts. An intent-to-treat analysis will be conducted with mixed-effects regression to test between-group differences in urge to drink after completing the task, nested within individuals. We will use a random-effects mixed modeling approach using maximum likelihood estimation to test differences in mean craving and drinking outcomes (i.e., alcohol consumption) between baseline and post-experiment. We will test differences in alcohol consumption between baseline and one-month follow-up. Participants will be modeled as random factors and the group allocation will be a fixed factor. Maximum likelihood estimation will provide unbiased estimates assuming missingness at random.¹³

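### The 1-month drinking outcome is defined by daily reports that are not scheduled at 1 month, and the TLFB taken then is named in neither statistical section

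*Combined protocol and SAP*

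**What the plan says.** Specific Aim 2 hypothesises lower consumption in the experimental group "during the 2-week intervention phase and at 1-month follow-up". The outcome definition in Statistical Design and Power covers both time points with one instrument: "decrease in number of standard drinks (amount) from baseline to 2-week intervention phase and at 1-month follow-up measured by daily reports of" the previous day's standard drinks.

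On data collection, the EMA Assessment Period section states: "The current study will employ a 1-week baseline EMA period followed by a 2-week experimental EMA protocol". Within that period "participants will be instructed to initiate a morning assessment each day to assess behaviors", and the previous-day drinking question is one of its items. For the two intervention weeks the plan says: "During, the experimental phase, the same assessments will be administered". The table of compensation for in-vivo assessments lists the morning assessments day by day and ends at Experiment Day 14.

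For follow-up, the Post-Experiment Assessment paragraph says that "participants will complete the TLFB over a video call at a 1-month follow-up". The same instrument is used at the start: under Baseline Visit, "Interview measures include the Time Line Follow"-back (TLFB).

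The Statistical Analyses section says "We will test differences in alcohol consumption between baseline and one-month follow-up", and Statistical Design and Power repeats the intention. Neither section names the TLFB.

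**The concern.** The outcome definition and the assessment schedule do not fit together. The analysis plan assigns the 1-month time point an instrument that is not in use then, and it leaves out the instrument that is. An analyst who follows the definition literally has no 1-month data to put in the model. An analyst who substitutes the TLFB must choose the baseline value and the recall window without guidance from the plan.

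Alcohol consumption is one of the two primary outcomes listed in the Summary of the Protocol. The 1-month comparison is also the part of Aim 2 that speaks to whether any effect lasts after the task stops, which the section on impediments and future directions says the study will inform. Leaving the instrument, baseline and window to be settled after data are in hand weakens that result. If the TLFB at 1 month were set against the EMA reports from the baseline week, the reported change within each group would also contain the difference between a retrospective interview and a daily report.

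**Working it through.** **Step 1: count the scheduled daily reports.** The inputs come from the EMA Assessment Period section and the in-vivo compensation table.

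- Baseline: 7 days × 1 morning report = 7.
- Experimental phase: 14 days × 1 morning report = 14.
- Total: 7 + 14 = 21, the last on Experiment Day 14. Because the item asks about the previous day, that report covers drinking on Day 13.

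**Step 2: check whether any later daily report could be hidden in the schedule.** No sentence says outright that daily reporting stops, so the payment figures are a useful cross-check.

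| Component | Arithmetic (USD) | Result | Plan's figure |
|---|---|---|---|
| Morning, baseline | 7 × 2 + 10 | 24 | 24 |
| Morning, experiment | 14 × 2 + 15 | 43 | 43 |
| Morning, total | 24 + 43 | 67 | 67 |
| Random prompts | (7 × 4 + 10) + (14 × 4 + 15) = 38 + 71 | 109 | 109 |
| All EMA | 67 + 109 | 176 | 176 |
| Visits | 30 + 25 + 30 | 85 | 85 (table) |
| Everything | 176 + 85 | 261 | 261 |

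The maximum of USD 261 for completing everything is fully used by the 21 morning reports, the random prompts of the same three weeks, and the three visit payments. No paid daily report remains for the 1-month time point. (The Retention text gives a visit total of USD 75. Its own components, the table and the USD 261 maximum all agree with 85, so 85 is used here.)

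**Step 3: set definition against schedule.**

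| Aim 2 time point | Instrument in the outcome definition | Drinking measure scheduled |
|---|---|---|
| 2-week intervention phase | Daily previous-day reports | Daily previous-day reports, with a 7-day EMA baseline |
| 1-month follow-up | Daily previous-day reports | TLFB only, with a TLFB at the baseline visit |

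The first row is consistent. The second is not, so 1 of the 2 Aim 2 time points is affected.

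**Step 4: what an instrument mismatch would do.** Let D_g be the true change in arm g from baseline to 1 month. Let s_g be the additive difference between TLFB and daily reports in that arm. With an EMA baseline and a TLFB follow-up:

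- Observed change within arm g = D_g + s_g.
- Observed group-by-time contrast = (D_1 − D_0) + (s_1 − s_0).

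The within-arm change is off by s_g. The contrast between arms is off only by s_1 − s_0, which is zero when the shift is common to both arms. With a TLFB at both times and windows of equal length, this change of instrument does not arise in either quantity. The documents give no value for s_g, so no size is put on it.

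**The case against.** The strongest reply is that the intended instrument is obvious. The TLFB is the only drinking measure named at 1 month, one is taken at baseline, and both statistical sections state the 1-month test in its own sentence. Matching TLFB with TLFB is the natural choice. This has force: the data needed for a sound comparison are planned. It does not rescue the definition, which names a different instrument, and it does not supply the recall window. If the mention of daily reports is read as applying to the 2-week phase only, the analysis plan names no instrument for 1 month, and the text still needs correcting.

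A second reply is that Aim 2 compares arms, that the plan intends to examine intervention by study time, and that a shift of instrument common to both arms cancels there. This stands. A reader might infer that an EMA baseline would bias the treatment comparison. The documents give no reason to expect a shift that differs by arm, so that inference is not supported. The mixing of time and instrument applies to change within each group.

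A third matter is timing. A reader might infer that the starting date for counting the month is undefined, so that much of a TLFB window could fall inside the intervention phase. The documents do not support this. The study-design figure, which may show the timing, is not reproduced in the available text. The narrative and the payment sequence also place the follow-up after the post-experiment assessment. No overlap is claimed.

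**Conclusion.** The point holds as an inconsistency between the outcome definition and the schedule. As written, the 1-month drinking outcome cannot be computed: all 21 scheduled daily reports fall in the baseline and experimental phases, and none falls at 1 month. This affects one of the two Aim 2 time points. The TLFB collected at that time is absent from both statistical sections.

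That daily reporting ends at Experiment Day 14 is inferred from the stated length of the EMA period and the payment schedule. Nothing in the documents contradicts it.

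A reader might go further and conclude that the trial cannot test drinking at 1 month at all. That would be wrong, because a like-for-like instrument is planned at baseline and at follow-up. The flaw lies in the analysis text, not in the data collection. It should be corrected before the analysis, but it does not threaten the trial, and no sample-size or power figure depends on it.

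**What to change.** In Statistical Design and Power, split the drinking outcome into two definitions.

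- **2-week phase:** standard drinks from the daily previous-day reports, comparing the baseline week with the experimental phase. Keep these reports for this contrast only.
- **1-month follow-up:** standard drinks from the TLFB over a stated window lying wholly after Experiment Day 14. The baseline value is the baseline-visit TLFB over a window of equal length, and the test is group by time in the mixed model already planned.

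Make the matching sentence in Statistical Analyses say the same.

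No new visit or instrument is needed. If both TLFB interviews already cover the chosen window, the change is wording only. Otherwise it needs a small change to the recall period at one or both interviews.
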